Optimum Time for Extracorporeal Shock Wave Lithotripsy for Residual Stones after Percutaneous Nephrolithotomy: A Prospective Comparative Randomized Study

Protocol ID: FMBSUREC/02122025/[name]

Date: December 2, 2025

Introduction

Percutaneous nephrolithotomy (PCNL) is considered the gold standard for the treatment of large renal stones (1). However, residual fragments (RFs) are not uncommon, occurring in 10–30% of cases (2). Management of these fragments is essential, as they may serve as a nidus for recurrent stone formation, infection, or obstruction (3).

Extracorporeal shock wave lithotripsy (ESWL) is often used for treating such residual stones, yet there is no consensus regarding the optimal timing of ESWL following PCNL (4,5). Early ESWL may facilitate stone clearance before fragments become embedded or encrusted but might increase the risk of bleeding or infection due to incomplete renal healing. Conversely, delayed ESWL allows for better renal recovery but may permit stone growth or recurrent symptoms (4,6).

This study aims to determine the optimal timing of ESWL after PCNL to achieve the highest stone-free rate with minimal complications.

Aim of the Work

Primary Objective:

To compare stone-free rates between early and delayed ESWL after PCNL.

Secondary Objectives:

To compare complication rates between the two groups.

Methodology

Type of the Study:

Prospective, randomized, comparative clinical study.

Site of the Study:

Urology Department, Beni-Suef University Hospital.

Duration of the Study:

From December 2025 till December 2026.

Study Population:

Patients who underwent PCNL and were found to have residual renal stones ≤ 15 mm on postoperative imaging (CT or ultrasound).

Sample Size Technique:

Random consecutive sampling based on eligibility.

Sample Size Calculation:

Using Chi-square test to detect a 10% difference in stone-free rate (SFR) between groups.

Based on prior data showing $\text{SFR} \approx 93\text{--}95\%$.

Required sample:

214 patients per group at 90% power, $\alpha = 0.05$.

After adding 10% dropout:

238 patients per group \rightarrow Total sample size = 476 patients.

Inclusion Criteria:

- Age 18–70 years.
- Single or multiple residual renal stones ≤ 15 mm after PCNL.
- Normal renal function (serum creatinine < 1.5 mg/dL).
- No active UTI.

Exclusion Criteria:

- Bleeding disorders or anticoagulant therapy.
- Obstructed drainage or active sepsis.
- Stones > 15 mm or requiring secondary PCNL.

Study Procedures / Tools:

Randomization:

Patients will be assigned into two equal groups: Total number of patients 476 patients and will be randomized to 238 patients per group →

Group A (Early ESWL): ESWL within 7–14 days after PCNL.

Group B (Delayed ESWL): ESWL after 3–4 weeks.

ESWL Protocol:

Same lithotripter model for all patients.

Sedation as needed.

Standardized energy and frequency according to EAU guidelines.

Maximum of 3 sessions.

Follow-Up:

Ultrasound or CT 2 weeks after final ESWL session.

Stone-free status = no fragments >2 mm.

Outcome Measures:

Primary:

Stone-free rate at 3 months.

Secondary:

Complications (hematuria, fever, infection).

Pain score (VAS).

Need for secondary intervention (URS or PCNL).

Statistical Analysis:

SPSS version 26.

Continuous variables: mean \pm SD, Student's t-test.

Categorical variables: percentages, Chi-square test.

$P < 0.05$ considered significant.

Ethical Consideration:

The study protocol will be reviewed and approved by the Research Ethics Committee, Faculty of Medicine, Beni-Suef University before conducting the study.

Sufficient time will be allocated to each patient and their family to explain the procedure in detail, including discussions with other patients who have previously undergone the same procedure.

A comprehensive explanation of the research project will be provided to all participants prior to enrolment.

Written informed consent will be taken from all study participants before enrolment in the study.

The study followed the Declaration of Helsinki for research ethics standards.

References:

2. El-Nahas AR, et al. J Urol. 2012;187(5):1673–1677.
3. Tefekli A, et al. Eur Urol. 2008;53(1):184–190.
4. Diri A, et al. Urolithiasis. 2018;46(3):281–287.
5. Türk C, et al. EAU Guidelines on Urolithiasis. 2024.
6. Abdelhafez MF, et al. World J Urol. 2021;39(6):1827–1836.
7. Desoky et al. Arab J Urol. 2017;15:20–35.

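### Eligibility has no lower size limit, so patients with only ≤2 mm fragments can be randomised although they already meet the stone-free definition at entry

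*Protocol*

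**What the plan says.** Stone size at entry appears in three places in the Protocol, and each gives only an upper bound:

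- Study Population: patients "found to have residual renal stones ≤ 15 mm on postoperative imaging (CT or ultrasound").
- Inclusion Criteria: "Single or multiple residual renal stones ≤ 15 mm after PCNL".
- Exclusion Criteria: "Stones > 15 mm or requiring secondary PCNL".

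No other criterion, such as symptoms or a stated need for treatment, would keep out very small fragments. Sampling is described as consecutive among eligible patients, so the written criteria decide who enters.

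The primary outcome is "Stone-free rate at 3 months", and the Follow-Up section defines success as "Stone-free status = no fragments >2 mm".

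The sample size section describes its target as "Using Chi-square test to detect a 10% difference in stone-free rate (SFR) between groups". It cites earlier stone-free rates of about 93–95%, and arrives at 214 per group for 90% power at α = 0.05, raised to 238 per group (476 in total) for 10% dropout.

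**The concern.** The entry criteria and the endpoint use different size ranges, and the two overlap. A patient whose largest fragment is 2 mm or less is eligible, is assigned to early or delayed ESWL, and satisfies the stone-free definition before any treatment is given.

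Two things are at stake. First, unless their fragments grow past the threshold by 3 months, such patients are successes whichever arm they are in. They raise both rates and narrow the gap that the chi-square test has to detect. Second, the reported stone-free rate becomes a mixture of stones cleared and patients who had nothing above the threshold to clear. That is not quite what the primary objective asks.

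Eligibility and the endpoint definition are protocol content. An analysis plan could not repair this later except by leaving out randomised patients after the fact.

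**Working it through.** **Inputs from the Protocol.** Difference 10 percentage points (read as absolute); planning rate 93–95%; 214 evaluable per group; α = 0.05; power 90%; dropout 10%; equal allocation.

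**Assumptions the Protocol does not settle.** The test is two-sided. The 93–95% is the higher of the two rates, since adding 10 points to it would exceed 100%. The share f of randomised patients with only ≤2 mm fragments is unknown, so a range from 0 to 30% is shown.

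**Step 1: reproduce the plan's figure.** For 93% versus 83%, two-sided 0.05 and 90% power:

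- pooled-variance normal formula: 220 per group
- unpooled formula: 217 per group
- arcsine formula: 213 per group

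The stated 214 lies within this range. For 95% versus 85% the pooled formula gives 188. Dropout: 214 / (1 − 0.10) = 237.8, rounded up to 238 per group, and 2 × 238 = 476. The plan's arithmetic is in order, and 93% versus 83% is the pair closest to it.

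**Step 2: model the dilution.** Let p be an arm's stone-free rate among patients who enter with at least one fragment >2 mm, and suppose that every patient entering with only ≤2 mm fragments is still stone-free at 3 months. Then

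- observed rate in each arm = f + (1 − f)·p
- observed difference = (1 − f) × 10 points

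Example, f = 20% with 93% versus 83%: 0.20 + 0.80 × 0.93 = 94.4%; 0.20 + 0.80 × 0.83 = 86.4%; difference 8.0 points.

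**Step 3: power at 214 per group.** Exact power of the Pearson chi-square test without continuity correction, summing the two binomial distributions over all tables with p < 0.05:

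| f | Difference (points) | Power, base 93% vs 83% | Power, base 95% vs 85% |
|---|---|---|---|
| 0% | 10.0 | 90.1% | 94.4% |
| 5% | 9.5 | 88.4% | 93.2% |
| 10% | 9.0 | 86.3% | 91.7% |
| 20% | 8.0 | 81.5% | 87.9% |
| 30% | 7.0 | 75.4% | 82.7% |

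The normal approximation runs about 1 point lower (for f = 20%: 80.4% and 86.5%) and shows the same pattern.

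**Step 4: the same loss as sample size.** With the pooled formula and 93% versus 83%, the number per group for 90% power rises from 220 (f = 0) to 234 (5%), 248 (10%), 283 (20%) and 328 (30%).

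**The case against.** The case on the other side has four parts.

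*Such patients are not fixed successes.* A reader might infer that they cannot show any treatment difference and cannot benefit on the trial's endpoint. The Protocol does not support that. The outcome is status at 3 months, not at entry, and the Introduction itself says that delay may allow stones to grow. A small fragment could pass 2 mm and fail, possibly more often in one arm. These patients also contribute to the secondary outcomes. This stands: the formula in Step 2 is a limiting case in which none regrows.

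*The share may be small.* A reader might infer that power is bound to fall below 90%. That does not follow. The documents give no value for f, and such fragments may rarely be detected or recruited. At 95% versus 85%, power is still 91.7% with f = 10%. At 93% versus 83%, f = 5% costs less than 2 points (90.1 − 88.4 = 1.7). This stands too, although in that scenario there is almost no margin above 90% to begin with.

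*The planning rates may already contain such patients.* The Protocol does not describe the population behind the 93–95%. If it also had no lower limit, part of the dilution is already in the planning rates and the loss is smaller than shown. This stands as a caveat on size.

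*A patient with nothing above 2 mm arguably has no residual stone.* On that reading the text merely omits a clarification. It is not conclusive: the 2 mm threshold appears only under Follow-Up, and the Introduction uses stones and fragments for the same thing. Entry should not depend on each recruiter's reading.

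None of this removes the mismatch between the entry range and the endpoint threshold. It limits how much can be claimed about its effect.

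**Conclusion.** The point holds as an inconsistency between eligibility and endpoint that should be corrected. Patients with only ≤2 mm fragments may be randomised while already meeting the stone-free definition. If they stay below the threshold, they dilute the difference and make the stone-free rate partly a record of entry status.

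The size depends on f. Over f = 0 to 30%, power at 214 per group runs from 90.1% down to 75.4% for 93% versus 83%, and from 94.4% down to 82.7% for 95% versus 85%. These figures assume that all such patients remain stone-free and that the planning rates refer to patients with a fragment >2 mm. The Protocol confirms neither.

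It would go too far to call the comparison biased or the trial unsound on this account. Under the dilution model the effect is the same in both randomised arms, so neither arm is favoured; what is lost is sensitivity, by an unknown and possibly small amount. The sample size arithmetic itself is not in error. This is a change that should be made, not one on which the validity of the trial depends.

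**What to change.** Reconcile the Study Population and Inclusion Criteria with the endpoint definition. Both should require, on the baseline scan, at least one residual fragment above whatever threshold defines stone-free (at present >2 mm), with the existing 15 mm upper limit kept. The choice of threshold belongs to the investigators; the statistical requirement is only that entry and endpoint use the same one, so that nobody enters with the primary endpoint already met. With f = 0 the planned 214 per group needs no change on this account.

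If the investigators prefer to keep patients with smaller fragments, the Protocol should say why, state the expected share, and base the expected rates and sample size on that mix.

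The cost is a one-line amendment, best made before enrolment. Some screened patients become ineligible, so recruitment is slightly slower.

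### The primary endpoint may be read on ultrasound or CT at one 2 mm cut-off, with no rule for which patient gets which scan, so stone-free status can depend on the scan chosen

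*Protocol*

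**What the plan says.** The Outcome Measures section of the protocol gives the primary outcome as "Stone-free rate at 3 months". The only imaging described after treatment is in the Follow-Up section: "Ultrasound or CT 2 weeks after final ESWL session". The line after it sets the criterion, "Stone-free status = no fragments >2 mm", without distinguishing the two modalities.

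The protocol has no rule for who gets which scan, no requirement that the arms use the same one, no confirmatory CT after a negative ultrasound, and no named reader. It describes itself as a "Prospective, randomized, comparative clinical study" and does not mention blinding either way. The arms differ in when treatment is given: "Group A (Early ESWL): ESWL within 7–14 days after PCNL" against "Group B (Delayed ESWL): ESWL after 3–4 weeks".

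**The concern.** The imaging modality and the cut-off together define the primary endpoint. If ultrasound misses small fragments that CT would show, a patient with a 3–5 mm fragment counts as a success on one scan and a failure on the other. No analysis can recover a fragment that the chosen scan did not show, so this is not a detail that can be left to an analysis plan.

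Two consequences are possible:

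- **Same mix of scans in both arms.** Missed fragments push both observed rates up, the difference shrinks and power is lost. Neither arm is favoured.
- **Different mix.** The arm with more ultrasound looks better with no true difference, and the type I error rises above its nominal level.

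The second is possible because patients and operators will know when the lithotripsy was given. That is an inference from the design, since the protocol is silent on blinding. The protocol's Introduction also expects the arms to differ clinically: more bleeding or infection with early treatment, stone growth or recurrent symptoms with delay. If such events prompt a CT, the choice of scan follows the arm.

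**Working it through.** **Inputs from the protocol (Sample Size Calculation).** A 10% difference, read here as 10 percentage points; prior stone-free rate 93–95%; 214 per group; 90% power; α = 0.05, taken as two-sided; chi-square test.

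**The plan's own figure.** For 93 vs 83%, the usual formula with pooled variance gives 220 per group, with unpooled variance 217, and with the arcsine transformation 213, against the stated 214. Dropout: 214/0.90 = 237.8, so 238 per group and 476 in all. Exact chi-square power at 214 per group is 90% for 93 vs 83% and 94% for 95 vs 85%. The sample size therefore reproduces. It takes the difference to be measured without imaging error.

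**Assumptions not in the documents.** CT is perfect. Ultrasound detects a proportion Se of patients who have a fragment above 2 mm, with Se from 0.5 to 0.8. Specificity is 1. The share u of patients read by ultrasound is set as shown below.

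**Formula.** A patient who is not stone-free is recorded as stone-free only if read by ultrasound and missed:

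observed rate = p + (1 − p) × u × (1 − Se)

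**(a) Same mix in both arms, u = 0.5**

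For p = 0.95 and Se = 0.5: 0.95 + 0.05 × 0.5 × 0.5 = 0.9625. For p = 0.85: 0.85 + 0.15 × 0.5 × 0.5 = 0.8875. The other rows follow in the same way.

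| True rates | Se | Observed rates | Observed difference | Exact power, 214 per group |
|---|---|---|---|---|
| 95 vs 85% | no error | 95 vs 85% | 10 points | 94% |
| 95 vs 85% | 0.8 | 95.5 vs 86.5% | 9.0 points | 92% |
| 95 vs 85% | 0.5 | 96.25 vs 88.75% | 7.5 points | 85% |
| 93 vs 83% | no error | 93 vs 83% | 10 points | 90% |
| 93 vs 83% | 0.8 | 93.7 vs 84.7% | 9.0 points | 86% |
| 93 vs 83% | 0.5 | 94.75 vs 87.25% | 7.5 points | 79% |

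**(b) No true difference; CT in 70% of one arm (u = 0.3) and 30% of the other (u = 0.7)**

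Spurious difference = (1 − p) × (0.7 − 0.3) × (1 − Se).

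| True rate, both arms | Se | Spurious difference | Exact type I error |
|---|---|---|---|
| 93% | 0.5 | 0.07 × 0.4 × 0.5 = 1.4 points | 9.5% |
| 93% | 0.8 | 0.07 × 0.4 × 0.2 = 0.56 points | 5.4% |
| 95% | 0.5 | 0.05 × 0.4 × 0.5 = 1.0 point | 8.3% |
| 95% | 0.8 | 0.05 × 0.4 × 0.2 = 0.4 points | 5.3% |

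With the same mix in both arms, the spurious difference is zero and the type I error stays at about 5%.

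**The case against.** The strongest reply is that nothing shows any harm. The protocol says nothing on who orders or reads the scan, a masked reader is neither stated nor excluded, and no text suggests that scan use would differ by arm. The accuracy figures and the 70/30 split are assumptions. With a milder split of 55/45 and Se = 0.6, the type I error is 5.0% at a true rate of 94% and 5.4% at 85%, which is hardly inflated. All of this stands. It limits the size of the point, but the endpoint still has no fixed measurement rule.

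A reader might infer more than the documents support:

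- **That the trial is declared open and that clinicians aware of the arm choose the scan.** The protocol says neither. Only knowledge of the treatment timing can reasonably be inferred.
- **That the type I error is about 12%.** That needs a true rate of 85% in both arms (Se = 0.6, 70/30 split). The protocol expects 93–95%, where the same assumptions give about 7–8%.
- **That power falls to 68–88%, or to 35–66% if ultrasound specificity is 95%.** Both ranges, for 95 vs 85%, put every patient on ultrasound. That is a single-modality trial and does not measure the effect of a free choice.
- **That the same freedom at entry biases the comparison.** Eligible patients are those "found to have residual renal stones ≤ 15 mm on postoperative imaging (CT or ultrasound". That scan establishes eligibility, so it should precede assignment. The endpoint is status at follow-up, not change from baseline, so a mismatch within a patient does not by itself favour an arm.
- **That requiring CT would only replace a scan, with no extra visit or reader.** No 3-month scan is described and no reader is named, so this cannot be claimed.

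**Conclusion.** The point holds in a limited form. The protocol does address how the primary endpoint is measured, but fixes it badly: two modalities, one cut-off, no selection rule and no stated masking. Under the stated assumptions, an even mix of scans costs about 2–9 percentage points of power at 95 vs 85% and about 4–12 at 93 vs 83%. A 70/30 imbalance between arms at the protocol's expected rates gives a type I error of about 5–10%. These are illustrations, because the documents give neither scan accuracy nor expected scan use. Dilution is the likelier harm; bias between arms is possible but not shown.

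A related conflict affects the same endpoint. The only scan described is tied to the last treatment session (2 weeks after it), while the endpoint is set at 3 months, so it is unclear which scan supplies the primary result. The change is worth making, but the point does not invalidate the design.

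**What to change.** Amend the Follow-Up and Outcome Measures sections as follows.

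1. Name one imaging modality for the primary-endpoint scan and use it for every patient in both arms. CT is already permitted and suits a 2 mm cut-off. State that the reader does not know the arm.
2. Reconcile the scan 2 weeks after the final session with the 3-month endpoint, so that it is clear which scan gives the primary result.
3. If both modalities must stay, set a selection rule that depends on neither arm nor symptoms, record the modality for each patient, and add a sensitivity analysis by modality. This deals with imbalance between arms but not with the dilution.

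**Cost.** A protocol amendment; radiation and expense for patients who would otherwise have had ultrasound; and an arrangement for masked reading. Whether a further scan or visit is needed depends on how item 2 is settled.

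### The protocol makes no provision for reading the primary-outcome image masked to arm, although the treatment timing cannot be hidden and the endpoint turns on a 2 mm threshold

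*Protocol*

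**What the plan says.** Under Type of the Study the Protocol describes a "Prospective, randomized, comparative clinical study". Under Randomization the arms are "Group A (Early ESWL): ESWL within 7–14 days after PCNL" and "Group B (Delayed ESWL): ESWL after 3–4 weeks"; timing is the only planned difference between them.

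Under Follow-Up, imaging is "Ultrasound or CT 2 weeks after final ESWL session" and the success criterion is "Stone-free status = no fragments >2 mm". Under Outcome Measures the primary outcome is "Stone-free rate at 3 months". Under Statistical Analysis, categorical outcomes are compared by chi-square.

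The Protocol names no image reader and does not say what a reader may know. It does not mention masking of any party, and it does not call the trial open-label. The only site listed is a urology department.

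**The concern.** Patients and operators cannot be kept unaware of whether ESWL came one to two weeks or three to four weeks after PCNL. Masking can therefore protect the primary comparison mainly at the reading of the outcome image. That reading is a yes/no call at 2 mm, by CT or by ultrasound, which depends on the operator. As written, nothing stops someone who knows the arm from making the call.

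The stakes come from the expected rates. With stone-free rates in the mid-90s, few patients per arm are counted as failures, so a small number of readings that lean one way in one arm carries a lot of weight. A chi-square test cannot correct misclassification that differs by arm. The same problem would exist if every patient had the same imaging modality.

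Who reads the scan, and what the request shows, has to be settled before images are read. It is a matter of trial conduct and would not normally be left to a statistical analysis plan.

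**Working it through.** **Inputs from the Protocol (Sample Size Calculation, Statistical Analysis).** Stone-free rate 93–95%, difference 10% (read as percentage points), 90% power, alpha 0.05, 214 per group, 238 after 10% dropout, chi-square test.

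**Assumptions.** Two-sided test; Pearson chi-square without continuity correction; 214 evaluable per arm; the 93–95% belongs to the better arm (the Protocol does not say which). The shares of failures misread are also assumed, because the Protocol gives no misreading rate.

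**1. The plan's own figure.** For 93% versus 83% at 90% power, the pooled normal formula gives 220 per arm, the unpooled 217 and the arcsine 213. The stated 214 is close to these. 214/0.9 = 237.8, rounded up to 238. The sample size is not in dispute, and masking does not change it.

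**2. Expected failures per arm.** 214 × 0.07 = 15.0; 214 × 0.06 = 12.8; 214 × 0.05 = 10.7. That is about 11–15.

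**3. How many readings move equal arms to p < 0.05.** With a and b failures in arms of size n, X² = (a − b)² × 2n / [(a + b)(2n − a − b)], compared with 3.84.

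| Failures in each arm | Moved in one arm | X² | p |
|---|---|---|---|
| 15 | 8 | 64 × 428 / (22 × 406) = 3.07 | 0.080 |
| 15 | 9 | 81 × 428 / (21 × 407) = 4.06 | 0.044 |
| 13 | 8 | 64 × 428 / (18 × 410) = 3.71 | 0.054 |
| 13 | 9 | 81 × 428 / (17 × 411) = 4.96 | 0.026 |
| 11 | 7 | 49 × 428 / (15 × 413) = 3.39 | 0.066 |
| 11 | 8 | 64 × 428 / (14 × 414) = 4.73 | 0.030 |

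So 8–9 readings in one direction are needed, which is 60–73% of that arm's failures (9/15 to 8/11).

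**4. Type I error with no true difference.** If the true failure rate is f in both arms and a share k of one arm's failures is read as stone-free, that arm's observed failure rate is f(1 − k). The rejection probability is the sum, over all pairs of failure counts with X² > 3.84, of Bin(214, f) × Bin(214, f(1 − k)).

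| Share k misread in one arm | Patients moved, 214 × f × k | SFR 93% | SFR 94% | SFR 95% |
|---|---|---|---|---|
| 0 | 0 | 0.048 | 0.048 | 0.048 |
| 10% | 1.1–1.5 | 0.057 | 0.055 | 0.055 |
| 25% | 2.7–3.7 | 0.112 | 0.102 | 0.094 |
| 50% | 5.4–7.5 | 0.364 | 0.319 | 0.274 |

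If the same share is misread in both arms, type I error stays at 4.7–5.0%, even at 50%.

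**5. Power with a true 10-point difference.** The same enumeration, with only the worse arm's failures misread.

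| Share misread, worse arm | Patients moved | 93 v 83 | 94 v 84 | 95 v 85 |
|---|---|---|---|---|
| 0 | 0 | 0.901 | 0.923 | 0.944 |
| 10% | 3.2–3.6 | 0.790 | 0.831 | 0.873 |
| 25% | 8.0–9.1 | 0.516 | 0.587 | 0.665 |

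With 25% misread in both arms, power is 79–86%.

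**6. At 238 per arm** the picture is similar. Type I error is 9.9–12.2% at a 25% share and 30–40% at 50%; power falls from 93–96% to 57–72% at 25%.

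**The case against.** The strongest reply is that nothing on the page is wrong: the Protocol is silent, and silence does not mean that the reader knows the arm. That stands as a limit on the claim. A reader might infer that this is a declared open-label trial with an unmasked assessor, but the Protocol states neither. What can be said is that masked reading is not provided for, in a design where the treatment itself cannot be concealed.

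A reader might also infer that a few favourable readings could decide the trial. The arithmetic does not support this as a general statement. From exactly equal arms it takes 8–9 one-sided reclassifications; three or four decide the result only if it already lies near the threshold, although an expected three or four roughly double the type I error.

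The harm also depends on bias that differs by arm. The Introduction sets out possible advantages and risks of both timings and names no favoured arm. Equal leniency leaves type I error close to nominal, and a 10% share in one arm hardly moves it. The loss of power in step 5 further requires the bias to favour the truly worse arm. Finally, only fragments near 2 mm are open to discretion, and the Protocol gives no figure for how many these would be. All of this stands: it limits the likely size of the problem without removing the gap.

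On the remedy, no independent radiology reader is mentioned anywhere, so one cannot be presumed. Ultrasound is measured live with the patient present, so removing dates from a request would not fully mask it.

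**Conclusion.** The concern holds in a limited form. The Protocol fixes the imaging and the threshold but leaves the primary-outcome reading open to detection bias that masking could reduce. The effect on type I error runs from negligible (5.5–5.7% at a 10% one-arm share) through material (9–11% at 25%) to severe (27–36% at 50%). Power under a true 10-point difference falls to 79–87% or 52–67% when 10% or 25% of the worse arm's failures are misread.

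These figures rest on the assumed shares, on bias in one direction in one arm, on 214 evaluable patients per arm and on the uncorrected two-sided test. They show how sensitive the result is and do not predict what will happen. The gap does not show that the reading will be biased or that the sample size is wrong. It justifies an inexpensive improvement before outcome images are read.

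**What to change.** Add to Follow-Up, for whichever image determines the primary outcome:

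- Whoever already reads the image does so without knowledge of the arm. Arm, PCNL date and ESWL dates are removed from the imaging request.
- The largest residual fragment is recorded in mm before the arm is disclosed. Stone-free status for the primary analysis is derived from that measurement.
- Where ultrasound is used, the person scanning is a member of existing staff who did not deliver that patient's ESWL, and the patient is asked not to disclose the timing.

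The cost is a few sentences in the Protocol, coding of imaging requests, and keeping any reading by the treating team out of the primary endpoint. It needs no extra scan, does not change the sample size and does not affect treatment. Its limit is that masking of live ultrasound will be partial, because the patient is present and knows the timing.

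### The primary outcome is set at 3 months with no stated origin, but the only scan listed falls 2 weeks after the last ESWL session; the two must be reconciled

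*Protocol*

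**What the plan says.** Under Outcome Measures, the primary outcome is "Stone-free rate at 3 months". No origin is given: it could be PCNL, randomisation, or the first or last ESWL session.

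Under Follow-Up, the one imaging assessment listed is "Ultrasound or CT 2 weeks after final ESWL session". The next line defines the endpoint: "Stone-free status = no fragments >2 mm". No 3-month visit or scan appears anywhere in the protocol.

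Three further statements determine when that scan falls:

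- Randomization: "Group A (Early ESWL): ESWL within 7–14 days after PCNL" and "Group B (Delayed ESWL): ESWL after 3–4 weeks". The second does not repeat the anchor.
- ESWL Protocol: "Maximum of 3 sessions", with no interval between sessions.

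Sample Size Calculation plans "214 patients per group at 90% power" for a 10% difference, citing prior stone-free rates of about 93-95% without the time at which they were measured.

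**The concern.** The protocol gives two times for one primary measurement, and on most readings they cannot be the same time. Site staff following Follow-Up would image each patient 2 weeks after the last session, and nothing would then prompt a scan at 3 months. The trial would have no planned value for its primary outcome, or the 2-week status would be reported under a 3-month label. If staff filled the gap ad hoc, scan times could differ between arms. A 3-month scan that was not done cannot be recovered afterwards.

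The scan date is also tied to treatment. Counted from PCNL, it depends on the arm, because time since PCNL is what is randomised. It also depends on the number of sessions, which may reflect how well treatment is working. Finally, the sample size rests on a stone-free rate that is not tied to either time point.

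**Working it through.** **1. The plan's own sample size.** Inputs from Sample Size Calculation: chi-square test, 10% difference (read as 10 percentage points), upper rate 93%, 90% power, alpha 0.05 (taken as two-sided). With the pooled-variance formula and mean rate 0.88:

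n = [1.96 × √(2 × 0.88 × 0.12) + 1.2816 × √(0.93 × 0.07 + 0.83 × 0.17)]² / 0.10² = [1.96 × √0.2112 + 1.2816 × √0.2062]² / 0.01 ≈ 220 per group.

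The unpooled formula gives 217 and the arcsine formula 213, so the stated 214 is reproduced to within a few patients. Dropout: 214 / 0.90 = 237.8, rounded up to 238, as stated. Exact power of the uncorrected chi-square test with 214 per group is 90.1% at 93 v 83 and 94.4% at 95 v 85. The sample size is sound for its stated inputs.

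**2. When the listed scan falls.** Day of scan after PCNL = day of first session + (k − 1) × interval + 14, for k sessions. The first session is on day 7-14 (A) or day 21-28 (B, assuming its window also runs from PCNL). The intervals are assumptions.

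| Sessions | Interval (assumed) | Group A | Group B |
|---|---|---|---|
| 1 | none | day 21-28 | day 35-42 |
| 3 | 7 days | day 35-42 | day 49-56 |
| 3 | 14 days | day 49-56 | day 63-70 |
| 3 | 21 days | day 63-70 | day 77-84 |
| 3 | 28 days | day 77-84 | day 91-98 |

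Taking 3 months as day 91, one-session patients are scanned early by 91 − 28 = 63 to 91 − 21 = 70 days (A), or 91 − 42 = 49 to 91 − 35 = 56 days (B): 7-10 weeks overall. For intervals up to 28 days, only Group B with three sessions 28 days apart reaches day 91.

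**3. Other origins.**

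- Last session: every scan is at day 14, which is 91 − 14 = 77 days (11 weeks) before month 3.
- First session: the scan is at 14 + (k − 1) × interval, at most 14 + 2 × 28 = 70 days.
- Randomisation: patients qualify on imaging after PCNL, so the count is no longer than from PCNL.

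**4. Difference between arms.** For the same number of sessions and the same interval, Group B is scanned between 35 − 28 = 7 and 42 − 21 = 21 days later after PCNL, so 1-3 weeks. At the midpoints it is 38.5 − 24.5 = 14 days. Time since the last session is 2 weeks for everyone.

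**5. What an early scan could do to power.** The documents give no 2-week clearance rate, so these are illustrations by assumption. Each is exact power with 214 per group, starting from 93 v 83:

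| Assumption at the scan | Rates | Power |
|---|---|---|
| Prior rates and gap already refer to an early scan | 93 v 83 | 90.1% |
| Both rates lower, 10-point gap kept | 90 v 80 | 83.4% |
| 10% of eventual clearers late in both arms | 83.7 v 74.7 | 63.6% |
| 20% late in both arms | 74.4 v 66.4 | 44.3% |
| 10% late in the better arm, 20% in the other | 83.7 v 66.4 | 98.8% |

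The rates are products, for example 0.93 × 0.90 = 0.837 and 0.83 × 0.80 = 0.664. Power may fall, hold or rise, depending on figures the protocol does not contain.

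**The case against.** The strongest defence is that Follow-Up never says its scan is the only one. The 3-month visit may simply have been left off the list, with the 2-week scan meant as an early check. That is possible, but the stone-free definition sits under the 2-week scan and no other is listed, so the reader cannot tell. It explains how the conflict may have arisen and does not remove it. Nor could a separate analysis plan cure it, since such a plan cannot analyse a scan that was never scheduled.

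The defence is right on several stronger readings that a reader might infer:

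- *That the 90% power is not delivered.* The stated figure reproduces from the stated inputs. A loss requires the rates or the gap at the scan to be less favourable than assumed, and the time point of the 93-95% is unknown.
- *That an early scan must shrink the difference.* It does so if late clearance is proportionally equal in both arms. If the worse arm clears more slowly, the gap widens.
- *That Group B's extra time since PCNL favours it.* The Introduction says delay may allow stone growth and suggests that early treatment may act before fragments become embedded. The net direction is not documented.
- *That patients are scanned at differing times on every clock.* Measured from the last session, all are scanned at 2 weeks. The times differ only when counted from PCNL, randomisation or the first session.

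**Conclusion.** The contradiction is real and needs correcting before the trial relies on this endpoint. The primary outcome has a time point with no origin, and the only listed scan does not measure it for nearly all patients on any of the origins considered. With one session the scan is 7-10 weeks before day 91 after PCNL, and 11 weeks before month 3 if counted from the last session. The between-arm shift of 1-3 weeks (2 on average) after PCNL holds for equal numbers of sessions and the same interval.

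These day counts assume that Group B's window runs from PCNL and that sessions are at most 28 days apart; neither is stated. The effect on power is a risk of unknown size and direction. The illustrations show how sensitive the design is to 2-week clearance and do not estimate a loss.

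**What to change.** State one origin for the 3 months that is common to both arms, for example randomisation or PCNL. Put the primary scan at that time, with a narrow window, in both Follow-Up and Outcome Measures. Report the scan 2 weeks after the last session as a secondary early stone-free rate. This changes no sample-size input: 214 evaluable and 238 randomised per group stand. It would still help to state when the 93-95% was measured.

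Alternatively, if the 2-week scan is the intended endpoint, rename the primary outcome as stone-free status 2 weeks after the final session, and confirm that the 93-95% and the stated power apply to that time.

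The first option costs a change to two protocol lines and a return visit with a scan at 3 months, which the stated outcome already implies. If the 2-week scan is kept, each patient has two scans. There is also a trade-off. With a PCNL or randomisation origin, Group B has about 2 weeks less clearance time after ESWL for the same number of sessions. From PCNL with one session, a day-91 scan falls 63-70 days after ESWL in Group B against 77-84 days in Group A. At the extreme of three sessions 28 days apart, Group B's last session is on day 77-84 and the scan follows only 7-14 days later. The protocol should acknowledge this when it fixes the origin.
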